7.6.1 Adverse Events

7.6.1.1 Definitions

Adverse Event

Per the International Conference on Harmonization (ICH) E2A Guidance, Clinical Safety Data Management: Definitions and Standards for Expedited Reporting ([ICH, 1995](#)), and 21 CFR 312.32 IND Safety Reporting, an AE is any untoward medical occurrence in a patient or clinical

investigation subject administered a pharmaceutical product and which does not necessarily have a causal relationship with this treatment.

The following information should be considered when determining whether or not to record a test result, medical condition, or other incident on the Adverse Events or Pre-existing Conditions case report form (CRF):

- From the time of informed consent through Day 1 prior to dosing, only study protocol-related AEs and serious adverse events (SAEs) should be recorded. A protocol-related AE is defined as an untoward medical event occurring as a result of a protocol mandated procedure.
- All baseline medical conditions present prior to dosing on study Day 1 should be recorded and assessed for grade or severity.
- All AEs (regardless of relationship to study drug) should be recorded from study Day 1 (during and post-dose) through the end of the safety reporting period (see Section 7.6.1.3). Complications that occur in association with any procedure (e.g., biopsy) should be recorded as AEs with assessed grade or severity whether or not the procedure was protocol mandated.
- Changes in baseline medical conditions and AEs (including changes in severity, frequency, or character) during the safety reporting period should be recorded.
- In general, an abnormal diagnostic or laboratory value should not be recorded as an AE unless it is associated with clinical signs or symptoms (i.e. assessed as clinically significant), requires an intervention, results in a serious adverse event (SAE), or results in study termination or interruption/discontinuation of study treatment. When recording an AE resulting from a diagnostic or laboratory abnormality, the medical condition or diagnosis rather than the abnormality itself should be recorded (e.g., record “anemia” rather than “low hemoglobin”).

Serious Adverse Event (SAE)

A serious adverse event (SAE) is any untoward medical occurrence that at any dose:

Fatal: Results in death.

Life threatening: Is life threatening.

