7.6.1.2 Procedures for Eliciting and Recording Adverse Events

Investigator and study personnel will report all AEs and SAEs whether elicited during subject questioning, or discovered during physical examination, laboratory testing and/or other means by recording them on the CRF and/or SAE form, as appropriate.

Eliciting Adverse Events

An open-ended or non-directed method of questioning should be used at each study visit to elicit the reporting of AEs.

Recording Adverse Events

The following information should be recorded on the Adverse Events and Pre-existing Conditions CRF:

- Description using standard medical terminology (with an effort to use the unifying or reached diagnosis), including onset and resolution dates
- Whether the AE met serious criteria
- Severity/Grade
- Relationship to study treatment or other causality
- Outcome

Diagnosis vs. Signs or Symptoms

In general, the use of a unifying or reached diagnosis is preferred to reporting of individual symptoms. Grouping of symptoms into a diagnosis should only be done if each component sign and/or symptom is a medically confirmed component of a diagnosis as evidenced by standard medical practice. If any aspect of a sign or symptom does not fit into a classic pattern of the diagnosis, report the individual symptom as a separate adverse event.

Important exceptions for this study are adverse reactions associated with the infusion of study drug. For infusion-related reactions, do not use the NCI CTCAE terms of ‘cytokine release syndrome,’ ‘acute infusion reaction,’ or ‘allergic or hypersensitivity reaction.’ Instead, record each sign or symptom as an individual AE. If multiple signs or symptoms occur with a given infusion-related event, each sign or symptom should be recorded separately with its own level of severity.

Recording Serious Adverse Events

For SAEs, record the event(s) on both the CRF and an SAE form.

The following should be considered when recording SAEs:

Death is an outcome of an event. Death, per se, is not a reportable event. The event that resulted in the death should be recorded and reported on both an SAE form and CRF.

For hospitalizations, surgical, or diagnostic procedures, the illness leading to the surgical or diagnostic procedure should be recorded as the SAE, not the procedure itself. The procedure should be captured in the narrative as part of the action taken in response to the illness.

Progression of the Underlying Cancer

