9.2.9.1 Treatment Emergent Adverse Events

Adverse events will be defined as treatment emergent if they are newly occurring or worsen following study treatment. The incidence of treatment-emergent adverse events and treatment-related adverse events will be tabulated. Adverse events will be classified by system organ class and preferred term using the Medical Dictionary for Regulatory Activities (MedDRA).

AEs will be listed and summarized by MedDRA preferred term, severity, and relationship to study drug. In the event of multiple occurrences of the same AE with the same preferred term in one subject, the AE will be counted once as the occurrence, using the event with highest severity grade and strongest causal relationship. The incidence of AEs will be tabulated by preferred term.

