6. ANALYTIC DEFINITIONS

Initial Treatment Period includes all assessments prior to the retreatment period or the start of new anti-cancer therapy, whichever occurs earlier. For subjects who will not be retreated, the initial treatment period will include assessments till the start of new anti-cancer therapy or the end of study, whichever occurs earlier.

Baseline Evaluation is the last available evaluation prior to receiving first dose of study drug. This will include any unscheduled evaluation prior to first dose. For subjects receiving retreatment, baseline for that period is the last available evaluation prior to receiving first dose of study drug for retreatment.

Change from Baseline is defined as the difference between the baseline value as defined above and the value at the respective time point. Negative values represent decreases from baseline; positive values will reflect increases from baseline.

Percent Change from Baseline is defined as the change from baseline divided by the baseline value times 100%. That is

$$100x (\text{Post-baseline value} - \text{baseline value}) / (\text{baseline value}).$$

Age at Baseline (in years) is defined from date of birth to date of first dose.

Last Evaluable Disease Assessment, for purpose of censoring, will be the last assessment with a response that is determined to be CR, PR, SD, PD, or Not Evaluable (NE).

Treatment-Emergent Adverse Event during this period is defined as any adverse event occurring on or after initiation of therapy and prior to the earlier of the start of retreatment period for those received Rova-T retreatment and the start of a subsequent anti-cancer therapy. Any adverse event with onset on or after the first dose of retreatment till the start of the next retreatment period or the start of a subsequent anti-cancer therapy will be considered treatment-emergent for that retreatment period.

Concomitant Medication is defined as a medication or treatment other than the study drug is considered concomitant if it is taken at any time on or after the first dose date. A medication taken prior to first dose date and continuing past first dose date is considered concomitant. Concomitant medications that stopped prior to first dose of retreatment will only be included in the initial treatment period. Medications started after the first of retreatment will be considered concomitant during the retreatment period.

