7.7.1 Treatment Emergent Adverse Events

All adverse events will be coded using the MedDRA dictionary. Safety analyses will involve examination of the incidence, severity, and type of treatment-emergent adverse events (TEAE) and serious adverse events as reported by the investigators. A treatment-emergent adverse event (TEAE)/treatment emergent serious adverse event is defined in Section 6. An applicable AE/SAE is considered ‘related’ if its relationship to study drug was judged by the investigator. Ongoing adverse events that have a change in severity, action taken with study drug, or outcome will be recorded multiple times with the

changes. If a subject has multiple occurrences of an adverse event with the same system organ class, the most severe event will be chosen. Similarly, if a subject has multiple occurrences of an adverse event with the same preferred term, the most severe event will be chosen. If a partial date does not provide enough information to determine the onset date relative to first dosing date, then the adverse event will be assumed as treatment-emergent, otherwise partial dates will be imputed relative to the first dose date. TEAEs will be summarized by system organ class and preferred term. These summaries will be presented by system organ class and preferred term for the following subsets:

- All TEAEs (All grades, and for maximum grade of 3 or 4)
- All TESAEs (All grades, and for maximum grade of 3 or 4)
- All TEAEs leading to study drug discontinuation (All grades, and for maximum grade of 3 or 4)
- All TEAEs leading to death

All drug-related TEAEs, and all drug-related TESAEs will also be summarized. The above tables will also be categorized by gender and age group (<65, \geq 65 years). For tables classifying TEAEs by severity, if a subject has multiple occurrences of an adverse event with the same system organ class, the most severe event will be chosen. Similarly, if a subject has multiple occurrences of an adverse event with the same preferred term, the most severe event will be chosen.

Adverse events of special interest (AESI) identified by the specific search criteria outlined in Appendix F will be summarized by System Organ Class (SOC) and Preferred Term (PT) [REDACTED]

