Tabulation of TEAEs will be based on subjects in safety analysis population. The number and percent of subjects with an adverse event will be displayed. In general, the denominator for the percent of subjects with an adverse will be the number of subjects in the safety analysis population or the number of subjects in safety analysis population within a subgroup if a subgroup is summarized.

All deaths that occur on study will be reported in a subject listing, which will include the primary cause of death and the number of days between the date of the last dose of study drug and death.

TEAE that occurred during retreatment period will be summarized separately for those who receive retreatment, provided there is sufficient number of subjects who received retreatment; otherwise listings will be provided. Adverse events that occurred after the start of subsequent anti-cancer therapy, if not included in the retreatment period, will be summarized separately by system organ class and preferred term, provided there is sufficient number of subjects; otherwise listings will be provided. Adverse events with onset prior to first dose date will be considered pre-treatment. All pre-treatment adverse events will be summarized by system organ class and preferred term, provided there is sufficient number of subjects; otherwise listings will be provided for pre-treatment adverse events. Listing of all AEs, SAEs, AEs leading to study drug discontinuation, and death will be reported.

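### The SAP defines treatment-emergent adverse events by timing alone and does not say which onset date a re-recorded event carries, so changed pre-existing conditions can be misclassified in either direction

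*SAP*

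**What the plan says.** The protocol and the SAP define the same term differently.

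- Protocol 9.2.9.1: "Adverse events will be defined as treatment emergent if they are newly occurring or worsen following study treatment".
- SAP section 6, initial period: "any adverse event occurring on or after initiation of therapy", ending at the earlier of retreatment and a subsequent anti-cancer therapy.
- SAP section 6, retreatment: "Any adverse event with onset on or after the first dose of retreatment", with a corresponding end point.

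SAP 7.7.1 refers back to section 6 for the definition and adds two rules:

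- On repeat records: "Ongoing adverse events that have a change in severity, action taken with study drug, or outcome will be recorded multiple times".
- On earlier events: "Adverse events with onset prior to first dose date will be considered pre-treatment". These are summarized or listed separately.

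On data collection, Protocol 7.6.1.1 requires the following:

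- "All baseline medical conditions present prior to dosing on study Day 1 should be recorded and assessed for grade or severity".
- "Changes in baseline medical conditions and AEs (including changes in severity, frequency, or character) during the safety reporting period should be recorded".

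Protocol 7.6.1.2 shows that adverse events and pre-existing conditions share a form: "The following information should be recorded on the Adverse Events and Pre-existing Conditions CRF".

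**The concern.** Subjects enter this trial with advanced small cell lung cancer, and many symptoms on the adverse event form may predate the first dose. Protocol 1.1.3 names fatigue and dyspnea among the most frequent events, and effusions and edema among the notable toxicities. Advanced lung cancer can produce the same findings. For such conditions, separating what was there before dosing from what became worse afterwards is the whole purpose of a treatment-emergent definition.

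The protocol's definition makes that separation and the SAP's does not. The rows at issue are post-dose records of pre-dose conditions. How they are classified depends on a date convention that the documents do not give. The incidence tables for all, serious and drug-related TEAEs, for those leading to discontinuation or death, and for the splits by sex and age all inherit the definition. With a single arm there is no control group in which the same misclassification would appear and could be set against it.

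**Working it through.** No arithmetic applies. The check is to take each course that a condition can follow, classify it under the protocol, and then classify it under SAP 6 and 7.7.1 for each of the two possible dating conventions. The grades are examples only.

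| Course of the condition | Protocol 9.2.9.1 | SAP, row dated at the change | SAP, row keeps first onset |
|---|---|---|---|
| Begins after first dose | TEAE | TEAE | TEAE |
| Present before dosing, worsens (Grade 1 to 3) | TEAE | TEAE | Pre-treatment |
| Present before dosing, improves (Grade 2 to 1) | Not a TEAE | TEAE | Pre-treatment |
| Present before dosing, same grade, only action or outcome changes | Not a TEAE | TEAE | Pre-treatment |
| Present before dosing, no change of any kind | Not a TEAE | No new row, pre-treatment | Pre-treatment |

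1. **Row dated at the change.** The third and fourth courses meet the timing rule in SAP 6 and fail the protocol's test, so they are over-counted. Counting each preferred term once per subject at worst severity does not remove them when the improvement is the subject's only post-dose record of that term.
2. **First onset kept.** Those two courses are correctly excluded by the pre-treatment rule, but so is the second. A pleural effusion that was Grade 1 before dosing and reached Grade 3 on drug would leave the TEAE tables, although Protocol Table 5-2 lists that grade of effusion as an unacceptable toxicity. This is an under-count.
3. **Comparison with the protocol.** Each convention gets at least one course wrong, so choosing a convention without restoring the grade comparison does not repair the definition.
4. **Retreatment.** The same fork applies to an event that began in the first course and is still present. Dated at the change, an improvement becomes a retreatment TEAE. With first onset kept, a worsening after the retreatment dose fails the onset condition.
5. **Other rules.** The defaults in SAP 7.7.1 and SAP 10 classify an event as treatment-emergent when its date cannot be resolved. They deal with missing dates, not with grade. No other part of the SAP as released restores a comparison with the pre-dose grade.

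**The case against.** The strongest defence is the pre-treatment rule in SAP 7.7.1. The SAP speaks of events occurring, not of records dated, and its partial-date rule also works from onset relative to first dose. A reader who takes onset to mean first onset will not count an improving baseline symptom as a TEAE. The retreatment definition is explicitly tied to onset, so an event carried over from the first course does not enter on its face. This defence stands as far as it goes. It means over-counting cannot be asserted as the result, but under that reading a worsened baseline condition is excluded, contrary to the protocol.

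Second, the repeat-record rule is written for ongoing adverse events. Protocol 7.6.1.1 treats baseline conditions separately and says only that changes in them are recorded, not that each becomes a new row; an improvement is also not obviously an untoward occurrence. Extending the rule to baseline conditions is an inference from the shared form and the duty to record changes of any kind. The inference is reasonable, but it is not stated.

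Third, the one-count-per-term rule means that repeat rows of an event that began on treatment do not inflate incidence in that period. This also stands and limits the point to conditions that predate the period's first dose.

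Finally, events classed as pre-treatment do not vanish from the report: they have their own summary or listing, and all on-study deaths are listed. They are still missing from the tables that readers use for toxicity rates.

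**Conclusion.** The point holds as a definition that departs from the protocol and gives a wrong classification under either available reading. It rests on two assumptions: that changes in pre-existing conditions produce rows on the shared form, and that the statistical programs follow SAP 6 and 7.7.1 as written.

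Two stronger conclusions are tempting and should not be drawn. A reader might infer that the TEAE rates are inflated. The documents do not support a direction, because the onset date of a re-recorded row is unstated and one of the two conventions gives an under-count. A reader might also infer that unchanged baseline conditions are swept in. They are not: a repeat row needs some change, and a condition without one keeps its pre-dose onset. The most that can be said is that rows with an unchanged grade but a changed action or outcome are at risk.

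No size can be given. It would need the prevalence of each condition before dosing, the share that change after it, and the share with no other qualifying event of the same term, none of which the documents provide. Primary efficacy is not affected. The change should be made because the main safety output otherwise rests on a definition that the protocol does not use.

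**What to change.** Amend SAP 6 and 7.7.1 as follows.

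- **Definition.** A TEAE is an event with onset on or after the first dose of the period, including recurrence after resolution, or a pre-existing event whose CTCAE grade after that dose exceeds its grade at that period's baseline. Keep the existing end of each period.
- **Baseline for retreatment.** Use the last evaluation before the first retreatment dose, as SAP 6 already defines it. Do not compare with the highest grade ever recorded: an event that was Grade 3 in the first course, settled to Grade 1 and returned to Grade 3 on retreatment would then be hidden.
- **Continuation rows.** Rows with the same or a lower grade, or with only a change in action or outcome, are linked to the event that they continue and are not separate TEAEs.
- **Dating.** State which onset date a re-recorded row carries.
- **Pre-treatment rule.** Reword it so that a pre-existing event that worsens after dosing counts as a TEAE.

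The cost is SAP wording and one derivation step. The grades are already collected under Protocol 7.6.1.1. The derivation needs a way to link rows that belong to the same event, which the documents do not describe; the sponsor should confirm that the database holds one or specify a matching rule.

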3.2.2 Dose Rationale

The chosen dose regimen, two doses of 0.3 mg/kg administered 6 weeks apart, is based on the safety and efficacy observed in a previous phase 1 study (SCRX16-001), where delayed and/or cumulative toxicities were observed with both q3wk and q6wk schedules and appeared to be related to total dose administered. The total dose was therefore capped at a total cumulative dose of 0.6 mg/kg and the finite dosing regimens of 0.2 mg/kg q3wk for a total of 3 doses (q3wk x 3) and 0.3 mg/kg q6wk for a total of 2 doses (q6wk x 2) were evaluated in expansion cohorts.

Because the intended mechanism of action of rovalpituzumab tesirine is to target cancer stem

cells and, more broadly, tumor-initiating cells, limiting the number of doses is hypothesized to affect anti-tumor response only minimally.

The 0.2 mg/kg q3wk x 3 and 0.3 mg/kg q6wk x 2 dosing regimens demonstrated comparable objective response and clinical benefit rates. Both regimens were tolerated, but the 0.3 mg/kg regimen demonstrated a trend towards lower rates of treatment-emergent adverse events (TEAE), related TEAEs, Grade 3/4 TEAEs and related Grade 3/4 TEAEs. In addition, although the 0.3 mg/kg regimen appeared to have a higher incidence of Grade 3/4 thrombocytopenia, such an AE was generally clinically manageable.

██████████ serosal effusions, which may be life threatening such as leading to pericardial tamponade. In addition, objectives responses preliminarily have appeared to be more durable in subjects treated with the 0.3 mg/kg regimen. Finally, the 0.3 mg/kg q6wk x 2 regimen is more conveniently administered than 0.2 mg/kg q3w x 3 and coincides with the timing of radiographic evaluation of tumor size. Therefore, 0.3 mg/kg q6wk x 2 is the chosen dose regimen for this study.

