7.6.1.3 Reporting Periods for Adverse Events and Serious Adverse Events

The safety reporting period for all AEs and SAEs is from study Day 1 (during and post-dosing) up to 30 days after the last study treatment dose. For those undergoing retreatment, the safety reporting period will also include retreatment study Day 1 (during and post-dosing) up to 30 days after the last study retreatment dose. However, all study protocol-procedure related AEs and SAEs are to be recorded from the time of informed consent. Additionally, all SAEs that occur after the safety reporting period that are considered study treatment-related in the opinion of the investigator should also be reported to the sponsor or its designee.

Each SAE must be followed until the SAE is Recovered/Resolved, Not recovered/Not resolved, Recovered/Resolved with sequelae, or the subject dies (the SAE may be assessed as ongoing at the time of death). SAE outcomes may not be possible to collect when a subject withdraws consent and/or is lost to follow-up. All non-serious AEs will be followed through the end of the safety reporting period. Certain non-serious AEs of interest should be followed until resolution, return to baseline, or study closure.

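### The drug-related, related-serious and fatal event tables leave out related events that begin once a new anticancer therapy has started, and no planned table gives their complete count

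*SAP*

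**What the plan says.** SAP Section 6 defines a treatment-emergent event for the initial course as one with onset from the first dose onward but "prior to the earlier of the start of retreatment period for those received Rova-T retreatment and the start of a subsequent anti-cancer therapy". For retreatment, an event counts from the first retreatment dose "till the start of the next retreatment period or the start of a subsequent anti-cancer therapy will be considered treatment-emergent for that retreatment period". Neither rule makes an exception for relatedness, seriousness or fatal outcome, and neither sets a fixed number of days after the last dose.

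SAP 7.7.1 builds its main tables on that definition: all treatment-emergent events, serious ones, those leading to discontinuation, those leading to death, and the drug-related and drug-related serious subsets. Events falling outside are handled as follows: "Adverse events that occurred after the start of subsequent anti-cancer therapy, if not included in the retreatment period, will be summarized separately". This separate display is organised at organ-class and preferred-term level, or becomes a listing if there are too few subjects. The same section promises listings of all AEs and SAEs. It also promises a listing of all on-study deaths with primary cause and days since last dose.

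Protocol 9.2.9.1 is wider: "Adverse events will be defined as treatment emergent if they are newly occurring or worsen following study treatment". Protocol 7.6.1.3 collects all AEs and SAEs "from study Day 1 (during and post-dosing) up to 30 days after the last study treatment dose", and adds that "all SAEs that occur after the safety reporting period that are considered study treatment-related in the opinion of the investigator should also be reported". Starting another therapy does not end that collection.

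**The concern.** The protocol asks investigators to report related serious events however late they occur, and to judge their relationship to study drug. The SAP then keeps some of those events out of the tables meant to show them, because another therapy had begun.

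This matters more here than in many trials. Protocol 3.2.2 records that in the phase 1 study "delayed and/or cumulative toxicities were observed with both q3wk and q6wk schedules", and Protocol 5.5.1 says serosal effusions can be life-threatening. There is no control arm against which to judge a related-event rate. Related fatal events are likely to be few, so one or two omissions could be a large share of the count. For the related tables the omission works in one direction: it lowers a count or leaves it unchanged.

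**Working it through.** The plan states no figure on this point, so there is none to reproduce. The check is a comparison of texts, followed by an illustration of size.

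**1. Where a related event goes under the SAP as written**

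- *Onset before new therapy or retreatment, at any time after the last dose:* treatment-emergent. The SAP has no 30-day cap, so a late related serious event in a subject who never starts new therapy stays in the main tables.
- *Onset on or after new therapy:* not treatment-emergent. It is absent from the drug-related, drug-related serious and leading-to-death tables. It goes to the separate summary or listing.

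**2. A traced example**

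Take a dose on Day 1, chemotherapy on Day 20, and a fatal pericardial tamponade on Day 26 judged related. Onset is 26 − 1 = 25 days after the dose, inside the 30-day reporting period. The event is missing from all three tables. It appears in the separate post-therapy summary or listing and in the deaths listing, and the death counts in overall survival (SAP 7.5.2).

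**3. How likely the within-30-day case is**

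The scheduled on-treatment scan falls on Days 36–42 of the cycle (Protocol 12.1, note 3). The earliest is 36 − 1 = 35 days after the dose. The end-of-treatment visit is normally 42 ± 3 days after the last dose, so 39 days at the earliest. Both lie beyond 30 days. Starting new therapy sooner requires early off-schedule progression or withdrawal. The likelier route is new therapy after one of these scans, followed by a related serious event reported under the open-ended rule in Protocol 7.6.1.3.

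**4. What the fallback outputs show**

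- SAP 7.7.1 states no split of the post-therapy summary by relatedness, seriousness, grade or fatal outcome.
- SAP Appendix G names no table for it, only a listing that pools pre- and post-treatment events (16.2_7.5).
- The serious and fatal event listings in Appendix G (16.2_7.2 and 16.2_7.4) are titled as treatment-emergent. The deaths listing (16.2_1.3) covers all deaths, but SAP 7.7.1 does not say that it will show relatedness.

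So no planned table adds the two parts into one complete related, related-serious or related-fatal count.

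**5. Illustration of size, on assumed inputs**

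Subjects affected = N × q × e. N = 123 is the planned number of DLL3-high third-line subjects (Protocol synopsis). q is the share who start new therapy while related events are still reportable. e is the share of those with a related event after that start. Both q and e are assumptions; the documents give neither.

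| q | e | N × q × e | Percentage points |
|---|---|---|---|
| 2% | 10% | 0.25 | 0.2 |
| 5% | 30% | 1.8 | 1.5 |
| 20% | 50% | 12.3 | 10.0 |

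The last row is an outer bound of the assumed grid, not an expectation. One omitted subject is worth 1/123 = 0.8 points. It is worth less in the overall safety tables, whose denominator is all dosed subjects and also includes those who are not DLL3-high or are fourth-line or later. An omission changes a row only if the subject has no other qualifying event in it, or none as severe in the tables by grade.

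**The case against.** The strongest reply is that the events are moved and not lost. That stands. SAP 7.7.1 gives them a separate summary or listing and promises listings of all AEs, SAEs and deaths. A reader might infer from Section 6 that the SAP discards these events or hides deaths; the documents do not support that.

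A second reply is that ending all-cause emergence at new therapy is a recognised attribution choice. Events after a new cytotoxic agent starts may be due to that agent, and counting them all could inflate the rates. Protocol 9.2.9.1 sets no end date and Protocol 9.2 leaves detail to the SAP. This also stands for the all-cause tables. It is weaker for events the investigator has already attributed to study drug.

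A third reply is that the case inside 30 days is rare, as the scan timing shows. A reader might infer that the main safety rates are materially understated during the reporting period. The documents give no rate that would support this.

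Finally, a reader might conclude that emergence should end with the 30-day reporting period. That would make the tables less complete in another way: recorded events after 30 days judged unrelated, which the SAP now keeps until new therapy or retreatment, would drop out.

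**Conclusion.** The point holds for related events with onset on or after the start of new anticancer therapy, in both the initial and the retreatment periods. The SAP's related, related-serious and leading-to-death tables would undercount any such events that the trial itself had collected and attributed to study drug, and no other planned table supplies the full count.

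The effect is probably small. Its size is unknown, and the figures above rest on assumed values of q and e. Subjects who never start new therapy are unaffected. The all-cause cut can stay as a defensible convention. This is a gap in tabulation that is cheap to close, and not evidence that safety data are being suppressed.

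**What to change.** 1. Keep the present SAP Section 6 window for all-cause treatment-emergent tables, and do not add a 30-day cap.
2. In the drug-related and drug-related serious tables, include every event the investigator judged related to study drug, whether or not new anticancer therapy has started. Do the same for a related-fatal count, shown as its own table or as a row beside the leading-to-death table.
3. Flag events with onset after new therapy, and keep the truncated version of each table as supportive. Start of retreatment still assigns an event to the retreatment course.
4. Split the post-therapy summary in SAP 7.7.1 by relatedness, seriousness, grade and fatal outcome, and add it to Appendix G.
5. State in Section 6 what counts as a subsequent anticancer therapy for this purpose, including whether the palliative brain radiotherapy described in Protocol 5.2.3.1 does.

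The cost is SAP wording, one flag in the adverse event dataset and a few extra outputs. No new data are needed, since dates of later therapies are already collected (Protocol 6.5). The downside is that a few events partly due to the next therapy enter the related tables, so those rates may be slightly higher. The flag and the supportive version let a reader see by how much.
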